#### 2. STUDY OBJECTIVES AND ENDPOINTS

#### **Table 1:** Study Objectives

#### **Primary Objective**

The primary objective of the study is to evaluate the clinical efficacy of oral apremilast 30 mg twice daily (BID), compared to placebo, in subjects with mild to moderate plaque psoriasis during the 16-week Placebo-controlled Phase.

#### **Secondary Objectives**

The secondary objectives are:

- To evaluate the safety and tolerability of apremilast 30 mg BID, compared with placebo, in subjects with mild to moderate plaque psoriasis
- To evaluate the effect of apremilast 30 mg BID compared with placebo on itch over the whole body caused by plaque psoriasis
- To evaluate the effect of apremilast 30 mg BID compared with placebo on Health-related Quality of Life (HRQoL)

#### **Exploratory Objective(s)**

**Table 2:** Study Endpoints

Endpoint	Name	Description	Timeframe
Primary	Static Physician Global Assessment (sPGA) 0/1	Proportion of subjects with an sPGA score of clear (0) or almost clear (1) and with at least a 2-point reduction from baseline	Week 16
Secondary	Body Surface Area (BSA)	Proportion of subjects who improved ≥ 75% in BSA from baseline	Week 16
	BSA	Change from baseline in affected BSA.	Week 16
	Psoriasis Area and Severity Index (PASI)	Change from baseline in total PASI score	Week 16
	BSA	Proportion of subjects who achieved BSA $\leq$ 3% for subjects with baseline BSA $>$ 3%	Week 16
	Whole body itch numeric rating scale (NRS)	Proportion of subjects with ≥4- point reduction (improvement) from baseline in the whole body itch NRS score among subjects with baseline whole body itch NRS ≥ 4	Week 16
	Scalp Physician Global Assessment (ScPGA)	Proportion of subjects with a ScPGA score of clear (0) or almost clear (1) with at least a 2-point reduction from baseline among subjects with baseline ScPGA score ≥ 2	Week 16
	Dermatology Life Quality Index (DLQI)	Change from baseline in DLQI total score	Week 16
	Safety	Type, frequency, severity and relationship of adverse events to investigational product (IP)	Throughout study (Day 0 to end of Observational Follow-up Phase)

**Table 2:** Study Endpoints (Continued)

Endpoint	Name	Description	Timeframe
Exploratory			

#### 3. OVERALL STUDY DESIGN

# 3.1. Study Design

This is a Phase 3, multicenter, randomized, placebo-controlled, double-blind study designed to evaluate the efficacy and safety of apremilast (CC-10004) in subjects with mild to moderate plaque psoriasis.

Approximately 574 subjects will be enrolled and randomized 1:1 to receive either apremilast 30 mg BID or placebo for the first 16 weeks. Subjects will be randomized based on a permuted block randomization using a centralized Interactive Response Technology (IRT). Randomization to apremilast arm or placebo arm will be stratified by baseline sPGA score (mild [2] or moderate [3]). Approximately 30% of subjects randomized will have a baseline sPGA score of mild (2) and approximately 70% of subjects will have a baseline sPGA score of moderate (3).

- Subjects randomized to the apremilast 30 mg BID treatment group will receive apremilast 30 mg tablets orally twice daily for the first 16 weeks
- Subjects randomized to the placebo treatment group will receive placebo tablets (identical in appearance to apremilast 30 mg tablets) orally twice daily for the first 16 weeks
- All subjects will receive apremilast 30 mg tablets orally twice daily after the Week 16 Visit through the end of the Apremilast Extension Phase of the study

The study will consist of four phases (Figure 1):

[figure not shown]
- Screening Phase up to 35 days
- Double-blind Placebo-controlled Phase Weeks 0 to 16
  - Subjects will be randomly assigned in a 1:1 ratio to either apremilast 30 mg BID or placebo.
- Apremilast Extension Phase Weeks 16 to 32
  - All subjects will be switched to (or continue with) apremilast 30 mg BID. All subjects will maintain this dosing through Week 32.
- Observational Follow-up Phase 4 weeks
  - Four-week Post-Treatment Observational Follow-up Phase for all subjects who complete the study or discontinue the study early

The blind should be maintained for persons responsible for the ongoing conduct of the study. Blinded persons may include but are not limited to: Clinical Research Physician, Clinical Research Scientist, Clinical Trial Manager, Study Statistician, Data Manager, Programmers, Clinical Research Associates.

After all subjects have completed the Week 16 Visit (or discontinued from the study), a Week 16 database restriction will be performed; the primary data analysis will be conducted and a Week 16 Clinical Study Report (CSR) will be generated. However, unblinded data will only be made

available to select Sponsor and Contract Research Organization (CRO) team members involved with analysis of the data and preparation of the Week 16 CSR. All other Sponsor, site, and CRO personnel directly involved with the conduct of the study, will remain blinded to treatment assignments until the final database lock at the conclusion of the study.

Figure 1: Study Design

The study will be conducted in compliance with the International Council for Harmonisation (ICH) of Technical Requirements for Registration of Pharmaceuticals for Human Use/Good Clinical Practice (GCP) and applicable regulatory requirements.

# 3.2. Study Duration for Subjects

Subjects who complete the entire study will spend a total of approximately 41 weeks in this clinical trial:

- Up to 35 days (5 weeks) in the Screening Phase
- Weeks 0 to 16 (16 weeks) in the Double-blind Placebo-controlled Phase
- Weeks 16 to 32 (16 weeks) in the Apremilast Extension Phase
- Four-week (4 weeks) Post-treatment Observational Follow-up Phase

#### 3.3. End of Trial

The End of Trial is defined as either the date of the last visit of the last subject to complete the post-treatment follow-up, or the date of receipt of the last data point from the last subject that is required for primary, secondary and/or exploratory analysis, as prespecified in the protocol, whichever is the later date.

# 4. STUDY POPULATION

# 4.1. Number of Subjects

Approximately 574 subjects with mild to moderate plaque psoriasis will be enrolled and randomized from investigator sites in Canada and the United States of America (USA).

#### 4.2. Inclusion Criteria

Subjects must satisfy the following criteria to be enrolled in the study:

- 1. Subject must be male or female, ≥18 years of age at the time of signing the informed consent form (ICF).
- 2. Subject must understand and voluntarily sign an ICF prior to any study-related assessments / procedures being conducted.
- 3. Subject is willing and able to adhere to the study visit schedule and other protocol requirements.
- 4. Subject must have a diagnosis of chronic plaque psoriasis for at least 6 months prior to signing the ICF.
- 5. Subject must have a diagnosis of mild to moderate plaque psoriasis at both Screening and Baseline as defined by:
  - a. sPGA score of 2-3 (mild to moderate)
  - b. BSA 2-15%
  - c. PASI score 2-15
- 6. Subject must be inadequately controlled with, or intolerant of at least one topical therapy (including topical corticosteroids, topical retinoids or vitamin D analog preparations, calcipotriene and betamethasone dipropionate ointment or foam, tacrolimus, pimecrolimus, or anthralin/dithranol) for the treatment of psoriasis at both Screening and Baseline.
- 7. Subject has not had prior exposure to biologics for the treatment of psoriatic arthritis, psoriasis, or any other indication that could impact the assessment of psoriasis.
- 8. Subject must be in good health (except for psoriasis) as judged by the investigator, based on medical history, physical examination, clinical laboratories, and urinalysis.
- 9. Subject must meet the following laboratory criteria:
  - a. White blood cell count  $\ge 3000/\text{mm}^3 \ (\ge 3.0 \times 10^9/\text{L})$  and  $< 14,000/\text{mm}^3 \ (< 14 \times 10^9/\text{L})$
  - b. Platelet count  $> 100.000/\mu L$  ( $> 100 \times 109/L$ )
  - c. Serum creatinine  $\leq 1.5 \text{ mg/dL}$  ( $\leq 132.6 \mu \text{mol/L}$ )
  - d. Aspartate aminotransferase (AST) (serum glutamic oxaloacetic transaminase [SGOT]) and alanine aminotransferase (ALT) (serum glutamic pyruvic transaminase [SGPT])  $\leq 2$  x upper limit of normal (ULN)
  - e. Total bilirubin  $\leq 2 \text{ mg/dL } (34 \mu\text{mol/L})$

10. Females of childbearing potential (FCBP) must have a negative pregnancy test at Screening and Baseline. While on investigational product and for at least 28 days after taking the last dose of investigational product, FCBP who engage in activity in which conception is possible must use one of the approved contraceptive options described below:

Option 1: Any one of the following highly effective methods: hormonal contraception (oral, injection, implant, transdermal patch, vaginal ring); intrauterine device (IUD); tubal ligation; or partner's vasectomy;

OR

Option 2: Male or female condom (latex condom or nonlatex condom NOT made out of natural [animal] membrane [for example, polyurethane]; PLUS one additional barrier method: (a) diaphragm with spermicide; (b) cervical cap with spermicide; or (c) contraceptive sponge with spermicide.

#### 4.3. Exclusion Criteria

The presence of any of the following will exclude a subject from enrollment:

- 1. Subject has any significant medical condition, laboratory abnormality, or psychiatric illness that would prevent the subject from participating in the study.
- 2. Subjects has any condition, including the presence of laboratory abnormalities, which would place the subject at unacceptable risk if he/she were to participate in the study.
- 3. Subject has any condition that confounds the ability to interpret data from the study.
- 4. Subject is pregnant or breast feeding.
- 5. Subject has hepatitis B surface antigen or anti-hepatitis C antibody positive at Screening.
- 6. Subject has active tuberculosis (TB) or a history of incompletely treated TB.
- 7. Subject has history of positive human immunodeficiency virus (HIV), or has congenital or acquired immunodeficiency (eg, common variable immunodeficiency disease).
- 8. Subject has active substance abuse or a history of substance abuse within 6 months prior to signing the ICF.
- 9. Subject has bacterial infections requiring treatment with oral or injectable antibiotics, or significant viral or fungal infections, within 4 weeks of signing the ICF. Any treatment for such infections must have been completed at least 4 weeks prior to randomization.
- 10. Subject has malignancy or history of malignancy except for:
  - a. treated (ie, cured) basal cell or squamous cell in situ skin carcinomas;

<sup>1 A female of childbearing potential is a sexually mature female who 1) has not undergone a hysterectomy (the surgical removal of the uterus) or bilateral oophorectomy (the surgical removal of both ovaries) or 2) has not been postmenopausal for at least 24 consecutive months (that is, has had menses at any time during the preceding 24 consecutive months).

<sup>2 The female subject's chosen form of contraception must be effective by the time the female subject is randomized into the study (for example, hormonal contraception should be initiated at least 28 days before randomization).

- b. treated (ie, cured) cervical intraepithelial neoplasia (CIN) or carcinoma in situ of the cervix with no evidence of recurrence.
- 11. Subject has prior history of suicide attempt at any time in the subject's life time prior to signing the informed consent and randomization, or major psychiatric illness requiring hospitalization within the last 3 years prior to signing the informed consent.
- 12. Subject has psoriasis flare/rebound (defined as a sudden worsening of psoriasis which requires administration of prohibited medications) within 4 weeks of signing the ICF or between the Screening and Baseline Visit.
- 13. Subject has current or planned concurrent use of the following therapies that may have a possible effect on psoriasis during the course of the treatment phase of the trial:
  - a. Topical therapy within 2 weeks of randomization (including but not limited to topical corticosteroids, topical retinoid or vitamin D analog preparations, tacrolimus, pimecrolimus, or anthralin/dithranol). An unmedicated skin moisturizer (eg, Eucerin®) will be also permitted for body lesions only. Subjects should not use these topical treatments within 24 hours prior to the clinic visit.
  - b. Conventional systemic therapy for psoriasis within 4 weeks prior to randomization (including but not limited to cyclosporine, corticosteroids, methotrexate, oral retinoids, mycophenolate, thioguanine, hydroxyurea, sirolimus, sulfasalazine, azathioprine, or fumaric acid esters).
  - c. Phototherapy treatment of body within 4 weeks prior to randomization (ie, ultraviolet B [UVB], psoralen and ultraviolet A [PUVA] radiation).
  - d. Use of any investigational drug beginning 4 weeks prior to randomization, or 5 pharmacokinetic/pharmacodynamic half-lives, if known (whichever is longer).
- 14. Subject has evidence of skin conditions that would interfere with clinical assessments.
- 15. Subject has prolonged sun exposure or use of tanning booths or other ultraviolet (UV) light sources.
- 16. Subject had prior treatment with apremilast.
- 17. Subject has history of allergy or hypersensitivity to any components of the investigational product (IP).

# 5. TABLE OF EVENTS

**Table 3:** Table of Events

	Screening	Placebo-controlled Treatment Phase							ast Extensi	Observational Follow-up	
Visit Number	1	Baseline a	3	4	5	6	7	8	9	10/ET b	11
Week	-5 to 0	0 (Day 1)	2 (± 4 days)	4 (± 4 days)	8 (± 4 days)	12 (± 4 days)	16 (± 4 days)	20 (± 4 days)	24 (± 4 days)	32 (± 4 days)	4 Weeks After Last Dose (± 2 weeks) c
Administrative/Demographics							•				
Informed consent d	X	-	-	-	-	-	-	-	-	-	-
Optional consent for research d	X	-	-	-	-	-	-	-	-	-	-
Demographics	X	-	-	-	-	-	-	-	-	-	-
Inclusion / Exclusion criteria	X	X	-	-	-	-	-	-	-	-	-
Medical history	X	-	-	-	-	-	-	-	-	-	-
Prior psoriasis medication	X	-	-	-	-	-	-	-	-	-	-
Prior / concomitant medications or therapies	X	X	X	X	X	X	X	X	X	X	X
Safety Assessments											
Height	X	-	-	-	-	-	-	-	-	-	-
Weight	X	X	X	X	X	X	X	X	X	X	X
Vital Signs	X	X	X	X	X	X	X	X	X	X	X
Complete Physical Examination	X	-	-	-	-	-	-	-	-	X	-
Pregnancy Test for FCBP and Contraception Education e	X	X	-	X	X	X	X	X	X	X	-
Hepatitis B and Cf	X	i	-	-	-	-	-	-	-	-	-
Clinical Laboratory Evaluations g	X	X	-	-	X	-	X	-	X	X	-

**Table 3:** Table of Events (Continued)

	Screening	Placebo-controlled Treatment Phase							Apremilast Extension Phase		
Visit Number	1	Baseline a	3	4	5	6	7	8	9	10/ET b	11
Week	-5 to 0	0 (Day 1)	2 (± 4 days)	4 (± 4 days)	8 (± 4 days)	12 (± 4 days)	16 (± 4 days)	20 (± 4 days)	24 (± 4 days)	32 (± 4 days)	4 Weeks After Last Dose (± 2 weeks) c
C-SSRS screening	X	-	-	-	-	-	-	-	-	-	-
C-SSRS since last visit	-	X	X	X	X	X	X	X	X	X	X
Psychiatric evaluation h	-	ı	-	1	-	-	-	-	-	-	•
Adverse events	X	X	X	X	X	X	X	X	X	X	X
Psoriasis Flare Assessment i	-	-	-	-	-	-	-	-	-	-	-
Clinical Efficacy Assessments											
sPGA	X	X	X	X	X	X	X	X	X	X	X
BSA	X	X	X	X	X	X	X	X	X	X	X
PASI	X	X	X	X	X	X	X	X	X	X	X
ScPGA j	X	X	X	X	X	X	X	X	X	X	X
NAPSP	-	X	-	-	X	-	X	-	-	X	-
Subject Rated Outcomes or Health	-related Qua	lity of Life	Assessmen	t							
Whole body itch NRS	-	X	X	X	X	X	X	X	X	X	-
DLQI	-	X	X	X	X	X	X	-	-	X	-
Pharmacodynamic Assessments (op	otional for s	ıbjects)	,								
Inflammatory Protein Biomarkers	-	X	-	-	-	-	X	-	-	-	-

**Table 3:** Table of Events (Continued)

	Screening		Placeb	o-controlled	l Treatmen	Apremil	ast Extensio	Observational Follow-up			
Visit Number	1	Baseline a	3	4	5	6	7	8	9	10/ET b	11
Week	-5 to 0	0 (Day 1)	2 (± 4 days)	4 (± 4 days)	8 (± 4 days)	12 (± 4 days)	16 (± 4 days)	20 (± 4 days)	24 (± 4 days)	32 (± 4 days)	4 Weeks After Last Dose (± 2 weeks) c
Dosing											
Dispense IP	-	X	-	X	X	X	X	X	X	-	-
Return and count IP tablets	-	-	-	X	X	X	X	X	X	X	-

BSA = body surface area; C-SSRS = Columbia-Suicide Severity Rating Scale; DLQI = Dermatology Life Quality Index; ET = Early Termination Visit; FCBP = females of childbearing potential; IP = investigational product; NAPSI = Nail Psoriasis Severity Index; NRS = Numeric Rating Scale; ScPGA = Scalp Physician Global Assessment; RNA = ribonucleic acid; sPGA = Static Physician Global Assessment.

<sup>a All baseline assessments must be completed prior to randomization and dispensing of IP.

<sup>b Visit 10 will serve as the Early Termination Visit for any subject who prematurely discontinues from the study.

<sup>c All subjects who complete the study or discontinue the study early will be asked to enter the Four-week Post-Treatment Observational Follow-up Phase.

<sup>d Written informed consent will be obtained by the Principal Investigator or designee prior to performing any study assessments. Optional consents for research include: RNA Gene Expression,

<sup>e FCBP: Serum pregnancy tests will be performed at the Screening and Early Termination/Visit 10. Urine dipstick pregnancy test will be performed at baseline, prior to dosing and at Visits 4, 5, 6, 7, 8, and 9. An unscheduled serum pregnancy test should be administered if the subject has missed a menstrual period or has a positive urine dipstick test. The investigator will educate all FCBP about the options for and correct use of contraceptive methods at the Screening and Baseline Visits and at any time when a FCBP's contraceptive measures or ability to become pregnant changes.

f Hepatitis B surface antigen and anti-hepatitis C antibody.

g Refer to Section 6.5, Clinical Laboratory Evaluations for details regarding hematology, clinical chemistries, and urinalysis parameters to be tested.

h Should be performed at any time during the study when suicidal thoughts or a suicide attempt is identified. See Section 6.5, Psychiatric Evaluation.

<sup>1 At any time during the study, a psoriasis flare may be reported as an adverse event, provided it meets the protocol definition. See Section 6.5, Psoriasis Flare Assessments.

<sup>j Post-baseline NAPSI and ScPGA assessments will only be performed for subjects with nail and/or scalp involvement, respectively, at Baseline.

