# 6.3. Observational Follow-up Period

For visits within the Observational Follow-up Phase, an administrative window of  $\pm$  2 weeks from the last dose of IP is permitted.

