#### 6.3.1. Safety Follow-up

All subjects will be followed for 28 days after the last dose of IP for AE reporting, as well as serious adverse events (SAEs) made known to the Investigator at any time thereafter that are suspected of being related to IP, as described in Section 10.1.

The following evaluations will be performed at the Follow-up Visit as specified in the Table of Events, Table 3.

- Concomitant medications or therapies evaluation
- Weight
- Vital signs
- Adverse event evaluation
- C-SSRS

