### • Columbia Suicide Severity Rating Scale (C-SSRS)

The C-SSRS (Posner, 2007) is a scale that captures the occurrence, severity, and frequency of suicide-related ideations and behaviors during the assessment period (Appendix F). The C-SSRS must be administered by appropriately trained site personnel. The C-SSRS will be completed at all study visits. At Visit 1 (Screening) the C-SSRS will be completed for the subject's lifetime history of suicidal ideation and behavior. At all other visits the C-SSRS will be completed for ideation and behavior since the previous visit.

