#### 8. CONCOMITANT MEDICATIONS AND PROCEDURES

Over the course of this study, additional medications may be required to manage aspects of the disease state of the subjects, including side effects from trial treatments or disease progression. Supportive care, including but not limited to antiemetic medications, may be administered at the discretion of the Investigator.

All concomitant treatments, including blood and blood products, used from 28 days prior to first dose of IP until 28 days after the last dose of IP, must be reported on the CRF.

For information regarding other drugs that may interact with IP and affect its metabolism, pharmacokinetics, or excretion, please see the current Investigators Brochure and/or local package insert.

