All AEs will be recorded by the Investigator from the time the subject signs informed consent until 28 days after the last dose of IP as well as those SAEs made known to the Investigator at any time thereafter that are suspected of being related to IP. All adverse events (serious/non-serious) will be recorded on the CRF and in the subject's source documents. All SAEs must be reported to Celgene Drug Safety within 24 hours of the Investigator's knowledge of the event by recording on the CRF and transmitting the data electronically. In the event the CRF is not available for transmission, a paper SAE Report Form will be sent directly to Celgene Drug Safety. The event must also be reported on the CRF once available.

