4.2.8.1. Treatment-emergent Adverse Event

An AE is a treatment-emergent AE (TEAE) if the AE start date is

- On or after the date of the first dose of investigational product (IP) and no later than 28 days after the last dose of IP for subjects who have completed study treatment or have discontinued early by the time of database cut, or
- On or after the date of the first dose of IP for subjects who are ongoing with study treatment at the time of database cut.

If the treatment-emergent status of an AE is unclear due to a missing/incomplete start date, it will always be considered treatment-emergent, unless shown otherwise by data. Date imputation rules for missing AE start dates are described in Appendix A1.

Adverse event started more than 28 days after the last dose of IP will not be considered as a treatment-emergent AE.

4.2.8.2. Treatment-emergent Adverse Event Leading to Drug Withdrawal, Drug Interruption, or Death, and Drug-related Treatment-emergent Adverse Event

A TEAE leading to drug withdrawal is a TEAE for which the investigator indicates that the action taken with respect to IP is withdrawn permanently. A TEAE leading to drug interruption is a TEAE for which the investigator indicates that the action taken with respect to IP is interrupted. A TEAE leading to death is a TEAE for which the outcome is fatal. Relationship to IP is based on the investigator's causality judgment; that is, a drug-related AE is an AE indicated by the investigator to have a suspected relationship to IP.

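### Safety data are to be collected to 28 days after the last dose, but the only scheduled post-treatment visit may be held on Day 14, and Table 3 and Section 6.3 anchor its window differently

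*Protocol*

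**What the plan says.** Several sections fix the length of follow-up at 28 days:

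- Protocol 6.3.1: "All subjects will be followed for 28 days after the last dose of IP for AE reporting".
- Protocol 10.1: recording runs "until 28 days after the last dose of IP as well as those SAEs made known to the Investigator at any time thereafter" and suspected to be related to study drug.
- Protocol 8: concomitant treatments are reportable when "used from 28 days prior to first dose of IP until 28 days after the last dose of IP".
- SAP 4.2.8.1: for subjects who have finished or stopped treatment, an event is treatment-emergent if it starts "no later than 28 days after the last dose of IP". SAP 5.1.1 gives the follow-up phase the same length.

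The schedule is looser. Table 3 has one visit in the Observational Follow-up Phase, Visit 11, at "4 Weeks After Last Dose (± 2 weeks". Adverse events, concomitant medications, C-SSRS, weight and vital signs are collected there, and no later visit or call is listed. Section 6.3 words the allowance as plus or minus "2 weeks from the last dose of IP is permitted". For the C-SSRS there is no fixed period: "At all other visits the C-SSRS will be completed for ideation and behavior since the previous visit".

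**The concern.** A visit on Day 14 is inside the Table 3 window. After it, the site still has to record adverse events and concomitant treatments for two more weeks, but the plan gives it no occasion to ask. Non-serious events in Days 15 to 28 reach the database only if the subject volunteers them. The SAP nevertheless counts treatment-emergent events over the full 28 days, so completeness would vary with when each site books the visit. The C-SSRS is also affected: with a Day 14 visit, its last look-back ends on that day. Separately, Table 3 and Section 6.3 do not give the same anchor for the window, so a site cannot tell from the text which dates are in range.

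**Working it through.** **The plan's own duration.** Protocol 3.2 gives about 41 weeks per subject. Screening 5 + placebo-controlled 16 + extension 16 + follow-up 4 = 41 weeks, so the stated figure is reproduced, and it counts follow-up as the full four weeks (28 days).

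**Window in Table 3.** 28 − 14 = Day 14 to 28 + 14 = Day 42 after the last dose.

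**Days without scheduled contact.** Uncovered days = max(0, 28 − visit day); share = uncovered days / 28.

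| Visit 11 held on | Uncovered days | Share of 28 days |
|---|---|---|
| Day 14 (earliest) | 14 | 50% |
| Day 21 | 7 | 25% |
| Day 28 | 0 | 0% |
| Day 42 (latest) | 0 | 0% |

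The documents give no distribution of visit dates, so the range is 0 to 14 days and no average can be derived from them.

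**Could another visit fill the gap?** Protocol 11.1 aims for the Early Termination Visit within 4 days of the last intake. It precedes Day 14 and cannot cover Days 15 to 28.

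**Table 3 against Section 6.3.** Table 3 applies the two weeks around Week 4. Section 6.3 applies them around the last dose, so its upper limit, read as written, is Day 14. The two windows share only Day 14.

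**Effect on the safety summaries.** SAP 11 defines the exposure-adjusted rate as 100 × (subjects with the event) / (total exposure in years), with exposure time taken from treatment duration. SAP 9.1.1 to 9.1.3 end treatment duration no later than the last dose. An event missed in Days 15 to 28 therefore leaves the numerator of both the incidence and the adjusted rate, while exposure time stays as it was. The error runs one way, downward.

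**Effect on the randomised comparison.** Subjects who complete Week 16 and continue reach Visit 11 only after the extension, when all are on apremilast. Those who leave during Weeks 0 to 16 enter follow-up from their randomised arm, and SAP 5.1.3 summarises them by that arm. Only these subjects carry the gap into the comparison with placebo. As an illustration of the upper size, if the 20% dropout in the sample-size section all occurred in that phase, they would number 0.20 × 574 ≈ 115; that timing is an assumption.

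**After the fix.** With Visit 11 on or after Day 28, uncovered days = 0.

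**The case against.** The strongest reply is that a visit window and a reporting duty are different things. Protocol 10.1 requires that "All AEs will be recorded by the Investigator from the time the subject signs informed consent until 28 days after the last dose of IP", and Section 10.5 requires all serious events in that period whatever their cause. A site that sees a subject on Day 14 and records nothing further has breached the protocol. This is correct. A reader might infer that recording closes at Visit 11 and that only related serious events are captured afterwards, but the documents apply that limit after Day 28, not after the visit. What remains is that the duty has no scheduled contact behind it.

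Other stronger readings also fail:

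- A reader might infer a 28-day C-SSRS window. None is stated; the scale covers the time since the previous visit. The supportable point is that no administration covers Days 15 to 28 after a Day 14 visit.
- A reader might treat the 28 days as person-time lost from a denominator. They only decide which events count as treatment-emergent; the SAP takes exposure from treatment duration.
- A reader might conclude that Section 6.3 leaves at least half of follow-up uncovered for everyone. A window on both sides of the last dose would allow a post-treatment visit before dosing ends, and the protocol calls the phase four weeks long and post-treatment. A drafting slip is the likelier explanation, though the text still has to be aligned.
- A reader might suppose that all subjects are affected, or that psoriasis rebound is under-counted. Visits from Day 28 lose nothing. Section 6.5 defines flare as worsening during treatment, and the documents set no post-withdrawal rebound endpoint.

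It is also fair to say that the effect on the placebo comparison is limited, as the working shows.

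**Conclusion.** The point holds as a gap in scheduled collection and a mismatch between two sections. Under Table 3 the worst case is 14 of 28 days (50%) resting on spontaneous report for adverse events and concomitant treatments, with no C-SSRS over the same days; the best case is no loss. The bias in TEAE incidence and exposure-adjusted rates is downward. Its size cannot be stated, because the documents give neither the distribution of visit dates nor an event rate after treatment. The conclusion rests on two readings: that Table 3 lists every scheduled contact, and that its window means four weeks plus or minus two. The primary efficacy analysis and its power are not involved.

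**What to change.** Reconcile Table 3 and Section 6.3 to a single wording anchored at 28 days after the last dose, under which Visit 11 cannot precede Day 28; a window of 0 to +14 days would do this and keeps the present outer limit of Day 42. State that a subject seen sooner is asked about adverse events and concomitant medications on or after Day 28. Check that the text agrees with protocol 6.3.1, 8 and 10.1 and SAP 4.2.8.1 and 5.1.1.

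The change is one line in Table 3 and one or two sentences in Section 6.3. No scheduled visit or assessment is added. The cost is that some follow-up visits take place up to two weeks later than they otherwise would, with an occasional extra query. Later visits would not inflate the TEAE count, because SAP 4.2.8.1 already excludes events that start more than 28 days after the last dose.
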